7.4.3 Dose Delays Due to Toxicity

- Participants who experience a DLT must have study treatment held. Participants who are required to permanently discontinue both study treatments are listed in Section 8.2. In addition, all Grade 2 hepatic, pulmonary, renal, gastrointestinal, and neurological AEs should be evaluated and managed per the toxicity management algorithms for immuno-oncology agents (see Appendix 9). Participants not meeting guidelines for permanent discontinuation will be

permitted to resume study treatment based on the criteria specified below in Section 7.4.4. Participants eligible to resume study treatment will resume study treatment at the treatment visit following their last received study treatment dose.

- The end of cycle tumor assessments (ie, CT/MRI, positron emission tomography [PET], etc) will continue on an every-8-week schedule relative to the participant's first dose regardless of any treatment delay incurred.

7.4.4 Criteria to Resume Treatment

Participants experiencing AEs not meeting criteria for permanent discontinuation as outlined in [Section 8.1](#) and [Section 8.2](#) may resume treatment with study treatment under the following criteria:

- Participants may resume treatment with study treatment when the study treatment-related AE(s) resolves to Grade ≤ 1 or baseline value with the following EXCEPTIONS:
 - Participants may resume treatment in the presence of Grade 2 fatigue.
 - Participants who have not experienced a Grade 3 study treatment-related skin AE may resume treatment in the presence of Grade 2 skin toxicity.
- Participants with Grade 2 uveitis or eye pain or blurred vision not meeting DLT criteria ([Section 7.4.1](#)) must resolve to baseline prior to resuming study treatment.
- Study treatment-related pulmonary toxicity, diarrhea, or colitis must have resolved to baseline before treatment is resumed.
- Participants with study treatment-related endocrinopathies adequately controlled with only physiologic hormone replacement may resume treatment.
- If the criteria to resume treatment are met, the participant should restart treatment at the next scheduled time point per protocol.
- The consideration to re-initiate study treatment under these exceptions will be made on a case-by-case basis after considering the overall benefit/risk profile and in consultation between the investigator and the study Sponsor. Any AE with clinical risk will be assessed on a case-by-case basis with the investigator and the BMS Medical Monitor to determine the risks and benefits of continuing on study treatment following resolution versus discontinuing study treatment permanently.
- If treatment with study treatment is delayed > 6 weeks, the participant must be permanently discontinued from study treatment, except as specified in [Section 7.4.2](#).

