7.4.1.1 Dose-limiting Toxicities

Dose-limiting Toxicities for DLT1 and DLT2 Periods

Nonhematologic DLT:

A. Hepatic, Nonhematologic DLT

Any of the following events will be considered a hepatic DLT:

- Any \geq Grade 3 elevation of AST, ALT, or total bilirubin
- Grade 2 AST or ALT with symptomatic liver inflammation (eg, right upper quadrant tenderness, jaundice, pruritus)
- AST or ALT $> 3 \times$ ULN and concurrent total bilirubin $> 2 \times$ ULN without initial findings of cholestasis (elevated serum alkaline phosphatase; eg, findings consistent with Hy's law or Food and Drug Administration definition of potential drug-induced liver injury [DILI])*

*Note that this special category of DLT uses ULN rather than Common Toxicity Criteria Grade for definition.

B. Nonhepatic, Nonhematologic DLT

Any of the following events will be considered a nonhepatic, nonhematologic DLT:

- Grade 2 or greater episcleritis, uveitis, or iritis
- Any other Grade 2 eye pain or blurred vision that does not respond to topical therapy and does not improve to Grade 1 severity within 2 weeks OR requires systemic treatment
- Any Grade 3 or greater nondermatologic, nonhepatic, nonhematologic toxicity will be considered a DLT with the following specific EXCEPTIONS:
 - Grade 3 or Grade 4 electrolyte abnormalities that are not complicated by associated clinical adverse experiences, last less than 48 hours, and either resolve spontaneously or respond to conventional medical intervention
 - Grade 3 nausea, vomiting, or diarrhea that lasts less than 48 hours and either resolves spontaneously or responds to conventional medical intervention
 - Isolated Grade 3 elevation of amylase or lipase not associated with clinical or radiographic evidence of pancreatitis
 - Isolated Grade 3 fever not associated with hemodynamic compromise (eg, hypotension, clinical or laboratory evidence of impaired end-organ perfusion)
 - Grade 3 endocrinopathy that is well controlled by hormone replacement
 - Grade 3 tumor flare (defined as pain, irritation, or rash that localizes to site of known or suspected tumor)
 - Grade 3 fatigue
 - Grade 3 infusion reaction that returns to Grade 1 in less than 6 hours

C. Dermatologic DLT

- Grade 3 rash if no improvement (ie, resolution to \leq Grade 1) after a 1- to 2-week infusion delay. Participants who have not experienced a Grade 3 study treatment-related skin AE may resume treatment in the presence of Grade 2 skin toxicity.

- Grade 4 rash of any duration.

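### Section 7.4.4 requires milder Grade 2 eye pain or blurred vision to return to baseline before restart, but leaves the DLT-level Grade 2 event to the looser Grade 1 default

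*Combined protocol and SAP*

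**What the plan says.** Four places in the combined protocol and SAP govern restart after a Grade 2 eye event.

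- **Section 7.4.1.1 (DLT definition).** Under the heading "Dose-limiting Toxicities for DLT1 and DLT2 Periods", one nonhepatic, nonhematologic criterion is "Any other Grade 2 eye pain or blurred vision that does not respond to topical therapy". Joined to this is a time condition, with systemic treatment as the alternative route: the event "does not improve to Grade 1 severity within 2 weeks OR requires systemic treatment". A separate line makes every uveitis of Grade 2 or above a DLT.
- **Section 7.4.3 (holds).** "Participants who experience a DLT must have study treatment held". Participants who do not meet the permanent-discontinuation guidelines are "permitted to resume study treatment based on the criteria specified below in Section 7.4.4".
- **Section 7.4.4 (restart).** The general rule is "Participants may resume treatment with study treatment when the study treatment-related AE(s) resolves to Grade" 1 or less, or to the baseline value. A later bullet sets baseline as the only threshold for "Participants with Grade 2 uveitis or eye pain or blurred vision not meeting DLT criteria". The bullet after it reads "Study treatment-related pulmonary toxicity, diarrhea, or colitis must have resolved to baseline before treatment is resumed", with no reference to DLT status.
- **Section 7.4.5 (permanent discontinuation).** The list includes Grade 3 uveitis and, with some exceptions, any Grade 4 event. It names no Grade 2 eye event.

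**The concern.** A restart rule normally becomes stricter, or at least no looser, as the event gets worse. Here the DLT qualifier takes the worse Grade 2 eye events out of the stricter rule, and no visible text puts an equal or stricter one in its place.

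What is at stake is individual safety on restart. Take a participant whose Grade 2 blurred vision needed systemic treatment, or neither responded to topical therapy nor reached Grade 1 within 2 weeks. The text lets that participant restart both drugs with Grade 1 symptoms still present. A participant whose Grade 2 event settled with topical therapy must wait for baseline. The dose-escalation model and the efficacy and safety endpoints are not at stake.

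**Working it through.** No arithmetic bears on the rule itself. The check is to follow two Grade 2 events, each eye pain or blurred vision, through the text.

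| Step | Milder event (responds to topical therapy, no systemic treatment) | Worse event (no topical response and not Grade 1 within 2 weeks, or systemic treatment needed) |
|---|---|---|
| DLT under Section 7.4.1.1? | No | Yes |
| Held under the DLT rule of Section 7.4.3? | Not by that rule; other hold rules may apply | Yes |
| Listed in Section 7.4.5 for permanent discontinuation? | No | No |
| Covered by the baseline bullet of Section 7.4.4? | Yes | No, excluded by the qualifier |
| Restart threshold | Baseline | Grade 1 or less, or baseline |

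Next, a search for any other text that would set a threshold for the right-hand column.

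1. Section 7.4.2 repeats the general threshold of Grade 1 or baseline. Table 7.4.2-1 has no row for Grade 2 eye events.
2. Sections 7.4.3 and 7.4.4 point to Section 8 for discontinuation. Section 8.1 has no eye criterion and refers back to Section 7.4.5. Section 8.2 concerns withdrawal from the study.
3. None of the algorithm titles in Appendix 9 is ocular.
4. Parts of Section 7.7.1 are redacted, so an eye-specific instruction there cannot be excluded.

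Then, how far the inversion reaches.

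1. A DLT in Cycle 0 already bars Cycle 1 (Section 7.4.1), so the gap matters from Cycle 1 on.
2. If DLT status can exist only in the DLT periods named in the Section 7.4.1.1 heading, the gap is confined to the 4-week combination window in Part 1. Section 5.1.2.2 applies the DLT criteria to toxicities in Part 2, and Section 7.4.1 speaks of events that meet the DLT definition at any time. Both favour the wider reading but do not settle it.
3. If the qualifier attaches to blurred vision alone, eye pain is already under the baseline rule and only blurred vision is affected.
4. DLT counts do not change under any reading. The events concerned are already DLTs when the restart question arises.

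**The case against.** The strongest reply is that DLT-level eye events were never expected to restart routinely, so the qualifier simply marks off the events for which restart is a live question. Section 7.4.1 names permanent discontinuation among the possible consequences of meeting the DLT definition. The example in Section 7.4.5 of a delay that may be extended concerns immune-related events that are not DLTs. This is a coherent account of intent, but it is inference. Section 7.4.1 offers interruption and dose modification as alternatives, Section 7.4.3 expressly provides a route back after a DLT hold, and no visible text stops treatment for these events. If that was the intent, Section 7.4.5 lacks an entry.

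A second reply is that discretion covers the gap. Section 7.4.4 calls for case-by-case assessment of any event with clinical risk, Section 7.4.2 describes its criteria as guidelines and allows more conservative handling, and Section 8.1 lets the investigator stop treatment. This stands as mitigation: Grade 1 is a minimum condition, not an instruction to restart. It does not supply a threshold, and for the milder event the plan chose to fix one.

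A reader might also infer more than the text supports:

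- **That failing topical therapy is enough to drop an event to the looser rule.** It is not. Without systemic treatment, the event must also fail to reach Grade 1 within 2 weeks.
- **That Grade 2 uveitis drops to the looser rule too.** Every Grade 2 uveitis is a DLT, so applying the qualifier to it would leave the word with no effect. It is better read as already under the baseline rule, though the wording is poor.
- **That planned enrolment measures the problem.** It shows how widely the rule could apply, not how many participants would be affected.

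**Conclusion.** The point holds as a minor drafting defect in a safety rule. By the text, Grade 2 eye pain or blurred vision that meets DLT criteria may restart at Grade 1, while the milder Grade 2 event must reach baseline.

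The conclusion rests on two assumptions: that the qualifier applies to eye pain as well as blurred vision (otherwise it holds for blurred vision alone), and that the redacted text contains no eye-specific restart rule. The two readings of DLT change how far the rule reaches, not its direction.

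The number affected cannot be estimated, because the documents give no ocular event rate. It is likely to be small: a participant must have a DLT-level Grade 2 eye event, improve to Grade 1 but not to baseline, and be cleared to resume after individual review. The documents do not support a claim that such participants would routinely be restarted.

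**What to change.** Delete the DLT qualifier from the Section 7.4.4 bullet, so that any Grade 2 uveitis, eye pain or blurred vision must return to baseline before study treatment restarts. This also removes the doubt over uveitis. If DLT-level Grade 2 eye events were meant to end treatment, list them in Section 7.4.5 instead. Restart after Grade 3 eye events is a separate question and need not be changed here.

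The cost is one sentence in an amendment and no new procedures. The downside is a few longer holds, some of which may reach the 6-week limit. For an event that becomes a DLT by failing to improve within 2 weeks, the time left to reach baseline depends on when the hold began, which is an assumption here:

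- held from onset: 6 − 2 = 4 weeks;
- held from the point at which the DLT is declared: 6 weeks.

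Section 7.4.5 allows extensions by agreement with the Medical Monitor, so a participant who is benefiting need not be lost to the limit.

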7.4.5 Guidelines for Permanent Discontinuation Secondary to Adverse Events

Participants will be required to permanently discontinue both study treatments for the following AEs:

- Clinical deterioration, as assessed by the investigator
- Grade 3 infusion reaction that does not return to Grade 1 in less than 6 hours
- Grade 3 pneumonitis, bronchospasm, neurologic toxicity, uveitis, or myocarditis
- Life-threatening skin toxicity (toxic epidermal necrolysis)

- Any Grade 4 AE; however, an exception may be made for the following upon consultation between the investigator and BMS Medical Monitor:
 - Grade 4 electrolyte abnormalities < 72 hours in duration
 - Grade 4 neutropenia < 7 days in duration
 - Grade 4 lymphopenia
 - Grade 4 increase in amylase or lipase that is not associated with clinical or radiographic evidence of pancreatitis
- Abnormal liver function tests meeting criteria for a potential DILI.
- Any dosing delay lasting > 6 weeks will be cause for permanent discontinuation. Extensions to the period of dose delays may be granted for individual participants on a case-by-case basis after specific consultation and agreement between the investigator and BMS Medical Monitor in settings where benefit/risk may justify continued study treatment (eg, participant deriving clinical benefit who requires prolonged steroid taper for management of non-DLT immune-related AEs or experiences delays for management of a non-treatment-related AE).
- Accordingly, dosing delays to allow for prolonged steroid tapers to manage study treatment-related AEs are allowed. Additionally, dosing delays > 6 weeks that occur for non-treatment-related reasons may be allowed if approved by the BMS Medical Monitor.
- The consideration to re-initiate study treatment under these exceptions will be made on a case-by-case basis after considering the overall benefit/risk profile and in consultation between the investigator and the Sponsor.
- Prior to re-initiating treatment in a participant with a dosing delay lasting > 6 weeks, the BMS Medical Monitor must be consulted.
- Tumor assessments should continue per protocol even if dosing is delayed.

All participants who discontinue the IP should comply with protocol-specified follow-up procedures as outlined in [Section 8.2](#). The only exception to this requirement is when a participant withdraws consent for all study procedures, including post-treatment study follow-up, or loses the ability to consent freely (eg, is imprisoned or involuntarily incarcerated for the treatment of either a psychiatric or physical illness).

If study treatment is discontinued prior to the participant's completion of the study, the reason for the discontinuation must be documented in the participant's medical records and entered on the appropriate case report form (CRF) page.

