8 DISCONTINUATION CRITERIA

8.1 Discontinuation from Study Treatment

Participants MUST discontinue IP (and non-IP at the discretion of the investigator) for any of the following reasons:

- Participant's request to stop study treatment. Participants who request to discontinue study treatment will remain in the study and must continue to be followed for protocol-specified follow-up procedures. The only exception to this is when a participant specifically withdraws consent for any further contact with him/her or persons previously authorized by participant to provide this information.
- Any clinical AE, laboratory abnormality, or intercurrent illness, which, in the opinion of the investigator, indicates that continued participation in the study is not in the best interest of the participant
- Termination of the study by BMS
- Loss of ability to freely provide consent through imprisonment or involuntarily incarceration for treatment of either a psychiatric or physical (eg, infectious disease) illness
- Inability to comply with protocol
- Discretion of the investigator
- Pregnancy
- Completion of study-required procedures
- Documented and confirmed PD as defined by RECIST v1.1 (see [Appendix 6](#)) unless participant meets criteria for treatment beyond progression ([Section 5.1.2.3](#))
- Clinical deterioration while receiving active study treatment that, in the opinion of the investigator, indicates that continued participation in the study is not in the best interest of the participant
- Protocol-defined reasons for discontinuation (see [Section 7.4.5](#))

Refer to the Schedule of Activities ([Section 2](#)) for data to be collected at the time of treatment discontinuation and follow-up and for any further evaluations that can be completed.

If study treatment is discontinued prior to the participant's completion of the study, the reason for the discontinuation must be documented in the participant's medical records and entered on the appropriate CRF page.

Discontinuation of the study treatment for abnormal liver tests should be considered by the investigator when a participant meets the conditions outlined in [Section 9.2.7](#).

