9.2.7 Potential Drug-induced Liver Injury

Wherever possible, timely confirmation of initial liver-related laboratory abnormalities should occur prior to the reporting of a potential DILI event. All occurrences of potential DILIs meeting the defined criteria must be reported as SAEs (see [Section 9.2](#) and [Appendix 3](#) for reporting details).

Potential DILI is defined as:

- AT (ALT or AST) elevation $> 3 \times \text{ULN}$
AND
- Total bilirubin $> 2 \times \text{ULN}$, without initial findings of cholestasis (elevated serum alkaline phosphatase),
AND
- No other immediately apparent possible causes of AT elevation and hyperbilirubinemia, including, but not limited to, viral hepatitis, pre-existing chronic or acute liver disease, or the administration of other drug(s) known to be hepatotoxic.

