APPENDIX 9 MANAGEMENT ALGORITHMS FOR IMMUNO-ONCOLOGY AGENTS

These general guidelines constitute guidance to the Investigator and may be supplemented by discussions with the Medical Monitor representing the Sponsor. The guidance applies to all immuno-oncology (I-O) agents and regimens.

A general principle is that differential diagnoses should be diligently evaluated according to standard medical practice. Non-inflammatory etiologies should be considered and appropriately treated.

Corticosteroids are a primary therapy for I-O drug-related adverse events. The oral equivalent of the recommended intravenous doses may be considered for ambulatory patients with low-grade toxicity. The lower bioavailability of oral corticosteroids should be taken into account when switching to the equivalent dose of oral corticosteroids.

[figure not shown]
Consultation with a medical or surgical specialist, especially prior to an invasive diagnostic or therapeutic procedure, is recommended.

The frequency and severity of the related adverse events covered by these algorithms will depend on the I-O agent or regimen being used.

Updated: 05-Jul-2016

GI Adverse Event Management Algorithm

Rule out non-inflammatory causes. If non-inflammatory cause is identified, treat accordingly and continue I-O therapy. Opiates/narcotics may mask symptoms of perforation. Infliximab should not be used in cases of perforation or sepsis.

[figure not shown]

Patients on IV steroids may be switched to an equivalent dose of oral corticosteroids (e.g. prednisone) at start of tapering or earlier, once sustained clinical improvement is observed. Lower bioavailability of oral corticosteroids should be taken into account when switching to the equivalent dose of oral corticosteroids.

Updated 05-Jul-2016

Renal Adverse Event Management Algorithm

Rule out non-inflammatory causes. If non-inflammatory cause, treat accordingly and continue I-O therapy

[figure not shown]

Patients on IV steroids may be switched to an equivalent dose of oral corticosteroids (e.g. prednisone) at start of tapering or earlier, once sustained clinical improvement is observed. Lower bioavailability of oral corticosteroids should be taken into account when switching to the equivalent dose of oral corticosteroids.

Updated 05-Jul-2016

Pulmonary Adverse Event Management Algorithm

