Rule out non-inflammatory causes. If non-inflammatory cause, treat accordingly and continue I-O therapy. Evaluate with imaging and pulmonary consultation.

[figure not shown]

Patients on IV steroids may be switched to an equivalent dose of oral corticosteroids (e.g. prednisone) at start of tapering or earlier, once sustained clinical improvement is observed. Lower bioavailability of oral corticosteroids should be taken into account when switching to the equivalent dose of oral corticosteroids.

Updated 05-Jul-2016

Hepatic Adverse Event Management Algorithm

Rule out non-inflammatory causes. If non-inflammatory cause, treat accordingly and continue I-O therapy. Consider imaging for obstruction.

Patients on IV steroids may be switched to an equivalent dose of oral corticosteroids (e.g. prednisone) at start of tapering or earlier, once sustained clinical improvement is observed. Lower bioavailability of oral corticosteroids should be taken into account when switching to the equivalent dose of oral corticosteroids.

[figure not shown]
*I-O therapy may be delayed rather than discontinued if AST/ALT ≤ 8 x ULN or T.bili ≤ 5 x ULN.

**The recommended starting dose for grade 4 hepatitis is 2 mg/kg/day methylprednisolone IV.

Updated 05-Jul-2016

Endocrinopathy Management Algorithm

Rule out non-inflammatory causes. If non-inflammatory cause, treat accordingly and continue I-O therapy. Consider visual field testing, endocrinology consultation, and imaging.

[figure not shown]

Patients on IV steroids may be switched to an equivalent dose of oral corticosteroids (e.g. prednisone) at start of tapering or earlier, once sustained clinical improvement is observed. Lower bioavailability of oral corticosteroids should be taken into account when switching to the equivalent dose of oral corticosteroids.

Updated 05-Jul-2016

Skin Adverse Event Management Algorithm

Rule out non-inflammatory causes. If non-inflammatory cause, treat accordingly and continue I-O therapy.

Patients on IV steroids may be switched to an equivalent dose of oral corticosteroids (e.g. prednisone) at start of tapering or earlier, once sustained clinical improvement is observed. Lower bioavailability of oral corticosteroids should be taken into account when switching to the equivalent dose of oral corticosteroids.

[figure not shown]
*Refer to NCI CTCAE v4 for term-specific grading criteria.

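### For liver tests that meet the potential-DILI criteria, Section 7.4.5 requires permanent discontinuation while the closing sentence of Section 8.1 leaves it to the investigator

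*Combined protocol and SAP*

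**What the plan says.** Section 7.4.5 opens its list with "Participants will be required to permanently discontinue both study treatments for the following AEs" and includes "Abnormal liver function tests meeting criteria for a potential DILI". The exceptions in that section belong to Grade 4 events and to long dosing delays. None is attached to the liver entry.

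Section 8.1 opens with "Participants MUST discontinue IP (and non-IP at the discretion of the investigator) for any of the following reasons". One entry in that list reads "Protocol-defined reasons for discontinuation (see" and then points to Section 7.4.5. The section closes with a separate sentence: "Discontinuation of the study treatment for abnormal liver tests should be considered by the investigator when a participant meets the conditions outlined in" Section 9.2.7.

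Section 9.2.7 defines potential DILI by three conditions that must all be met: ALT or AST above 3 × ULN; total bilirubin above 2 × ULN without initial cholestasis; and no other immediately apparent cause.

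Section 7.4.3 says that the participants who must stop both treatments permanently are listed in Section 8.2. Section 7.4.4, on resuming treatment, refers to Sections 8.1 and 8.2 for the permanent-discontinuation criteria.

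Appendix 9 describes its own status as follows: "These general guidelines constitute guidance to the Investigator and may be supplemented by discussions with the Medical Monitor representing the Sponsor". The footnote to its hepatic algorithm reads "I-O therapy may be delayed rather than discontinued if AST/ALT ≤ 8 x ULN or T.bili ≤ 5 x ULN".

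**The concern.** One laboratory pattern meets a mandatory instruction in one section and a discretionary one in another, and the protocol states no order of precedence between them. What is at stake is whether a participant with a possible serious liver signal is exposed again.

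The event is foreseeable. Section 3.3.1 reports gallbladder inflammation with raised GGT and ALT in dogs at 100 mg/kg/day (reversible). Section 3.3.2 names hepatitis among the immune-mediated effects of nivolumab, and reports one dose-limiting autoimmune hepatitis among 9 participants given a related IDO1 inhibitor at 100 mg daily with nivolumab.

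Two features of the design add weight. Section 5.1.5 counts clear discontinuation and dose-delay criteria among the reasons for having no Data Monitoring Committee. Table 4-1 makes adverse events leading to discontinuation part of the primary endpoint, so a rule that can be read two ways feeds into a reported count.

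**Working it through.** The plan gives no figure to reproduce. The check is a comparison of texts, followed by a comparison of thresholds.

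**Step 1: is the trigger the same?** Section 7.4.5 refers to the criteria for potential DILI without a section number. The closing sentence of Section 8.1 cites Section 9.2.7, which is the protocol's definition of potential DILI. I take both to mean Section 9.2.7.

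**Step 2: do the instructions agree?**

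| Text | Instruction when Section 9.2.7 is met |
|---|---|
| Section 7.4.5 | Permanent discontinuation of both treatments, required |
| Section 8.1, mandatory list (through its entry for Section 7.4.5) | Investigational product must be discontinued; Section 7 classes both drugs as investigational product |
| Section 8.1, closing sentence | Investigator should consider discontinuation |

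The first two agree. The third does not, and it stands in the same section as the second.

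**Step 3: do the cross-references settle it?** Section 7.4.3 points to Section 8.2, which covers withdrawal of consent and continued follow-up and contains no list of events. Section 7.4.4 points to Sections 8.1 and 8.2. Table 7.4.2-1 points to Section 8 as a whole. None of them names Section 7.4.5, where the list is. A reader who follows the usable pointer reaches Section 8.1, where the only sentence that mentions liver tests is the discretionary one.

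**Step 4: does the Appendix 9 footnote overlap?** Write A for AST/ALT and B for total bilirubin, in multiples of ULN. All cases below also need no initial cholestasis and no other apparent cause.

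- Potential DILI: A > 3 and B > 2.
- Footnote as printed: A ≤ 8 or B ≤ 5. The overlap is every potential-DILI case except those with both A > 8 and B > 5.
- Footnote read narrowly, with *and* in place of *or*: the overlap is 3 < A ≤ 8 with 2 < B ≤ 5.

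The regions overlap on either reading. Example: ALT 4 × ULN and bilirubin 2.5 × ULN, without cholestasis or another apparent cause. Section 7.4.5 requires permanent discontinuation, the closing sentence of Section 8.1 asks the investigator to consider it, and the footnote, if it applies to such a case, permits a delay.

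**The case against.** The best reply is that precedence can largely be worked out. The mandatory list in Section 8.1 takes in Section 7.4.5, and an instruction to consider does not cancel an instruction that something must be done. Table 7.4.2-1, Section 7.4.3 and Section 7.4.4 all put the permanent-discontinuation criteria ahead of dose reduction or resumption. This shows that a careful reader can reach the mandatory reading. It does not remove the conflict: those passages point to Section 8, 8.1 or 8.2, and the discretionary sentence remains in Section 8.1.

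A second reply is that sites do not act alone. Section 9 requires immediate safety concerns to be discussed with the sponsor to decide on continuation, and Section 7.4.4 brings in the Medical Monitor. The laboratory pattern is also a hepatic DLT under Section 7.4.1.1, Section 7.4.3 requires treatment to be held after a DLT, and Section 9.2.7 makes potential DILI reportable as an SAE. All of this stands. DLT and SAE capture do not depend on the disputed wording, and divergence between sites is possible rather than certain.

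A reader might infer that Appendix 9 is a proven third rule. The documents do not support that. The appendix is general guidance for all immuno-oncology agents, and its footnote does not name DILI. The figure it belongs to is not shown, so the row it modifies and any exclusion for DILI cannot be seen. Section 7.4.1 places the guidance on these algorithms in Section 7.7.1.4, which is not in the readable text. What can be said is that the thresholds overlap and the readable text contains no exclusion.

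**Conclusion.** The plan is wrong as written: it contradicts itself. The firm part is Section 7.4.5 and the mandatory list of Section 8.1 against the closing sentence of Section 8.1, made harder to resolve by pointers that miss Section 7.4.5. The Appendix 9 overlap is secondary and calls for clarification.

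The rule covers the whole planned enrolment of up to 298, and a reader might take that as the number affected. It is not. Only participants who meet all three conditions of Section 9.2.7 are affected, and the documents give no expected rate. A raised transaminase and bilirubin with another apparent cause is not potential DILI and falls outside the conflict.

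The effect on the endpoint is limited to the count of adverse events leading to discontinuation. Its size and direction cannot be derived from the documents. That sites may differ in practice is an inference from the wording. The conclusion assumes that Section 7.4.5 uses the Section 9.2.7 definition. Because re-exposure after a possible serious liver signal turns on this text, it should be settled before participants are treated under it.

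**What to change.** Reconcile Section 7.4.5, the closing sentence of Section 8.1 and the hepatic footnote of Appendix 9 to one rule for participants who meet Section 9.2.7, and state which text governs if they differ. In Section 7.4.5, cite Section 9.2.7 by number. Correct the references in Sections 7.4.3 and 7.4.4 so that they lead to the section that holds the permanent-discontinuation list. Which rule applies is for the sponsor's clinical team to decide, and this review takes no position on it.

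The cost is wording in Sections 7.4.3, 7.4.4, 7.4.5, 8.1 and Appendix 9. No procedure, visit or participant is added.
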